7. PLANNED ANALYSIS

Disposition of the patient population participating in the trial will be analysed by treatment groups and presented in the clinical trial report (CTR) as a frequency-distribution. The number of patients participating in the study by centre will also be analysed by treatment group and presented as a frequency distribution.

A frequency of patients with important PVs, also summarised by whether the IPV led to exclusion from the PPS, will be presented by treatment group for the treated set. The frequency of patients in different analysis sets and primary reason for exclusion will also be analysed for each treatment group on randomised set.

For in-text tables presenting descriptive analysis of the end-points and other variables, the set of summary statistics is: N (number of patient with non-missing values), mean, standard deviation (SD).

For the respective end-of-text tables, the set of summary statistics is: N / Mean / SD / Min / Median / Max.

For appendix tables, the set of summary statistics is: N / Mean / SD / Min / Q1 (lower quartile) / Median / Q3 (upper quartile) / Max.

Tabulations of frequencies for categorical data will include all possible categories and will display the number of observations in a category as well as the percentage (%) relative to the respective treatment group. Percentages will be rounded to one decimal place. The category *Missing* will be displayed if and only if there are actually missing values. Percentages will be based on all patients in the respective patient set whether they have non-missing values or not.

7.1 DEMOGRAPHIC AND OTHER BASELINE CHARACTERISTICS

Descriptive analysis of the following demographic variables measured at baseline will be presented on the TS population:

Gender, age (in years), age-groups, weight (kg), weight categories, BMI (kg/m^2), BMI categories, eGFR ($\text{ml}/\text{min}/1.73\text{m}^2$), eGFR categories, Metformin dose, baseline daily insulin dose, daily insulin dose per body weight (IU/kg), type of insulin, height (cm), waist circumference (cm), smoking-status and alcohol status. Categories for demographic and baseline characteristics are defined in [Section 6.4](#).

Descriptive analysis of the following baseline efficacy variables will be presented on the FAS population:

HbA_{1c}, HbA_{1c} categories, FPG (mg/dL), FPG categories,

time since diagnosis of diabetes.

A summary of the number of patients in each randomisation stratum per treatment will also be shown. This will be based upon the data received from the IRT provider.

7.2 CONCOMITANT DISEASES AND MEDICATION

Frequency distribution of patients with different concomitant diseases and medications (including the anti-diabetic therapies at screening) will be presented.

7.3 TREATMENT COMPLIANCE

Only descriptive statistics are planned for this section of the report. Frequency distribution of patients whether with compliance-level between 80% and 120% will be presented by visit (Week 0 to 4, Week 4 to 8, Week 8 to 12, Week 12 to 18 and Week 18 to 24).

7.4 PRIMARY ENDPOINT(S)

7.4.1 Primary efficacy analysis

The primary analysis will be performed on the FAS (OC) and patients will be assigned to the treatment they were randomised to. A REML-based MMRM approach is applied to compare the change in HbA_{1c} from baseline after 24 weeks of treatment.

The statistical model will be

$$\begin{aligned} \text{HbA}_{1c} \text{ change from baseline} = & \text{overall mean} + \text{baseline HbA}_{1c} + \text{treatment} + \text{type of insulin} \\ & + \text{week} + \text{week by treatment interaction} \\ & + \text{baseline HbA}_{1c} \text{ by week interaction} \\ & + \text{random error} \end{aligned}$$

This model includes effects accounting for the following sources of variation: ‘baseline HbA_{1c}’, ‘treatment’, ‘type of insulin (basal insulin or any permitted pre-mixed insulin)’, ‘week’, ‘week by treatment interaction’ and ‘baseline HbA_{1c} by week interaction’. ‘Treatment’, ‘type of insulin’, ‘week’ and ‘week by treatment interaction’ are fixed, categorical effects, and ‘baseline HbA_{1c}’ and ‘baseline HbA_{1c} by week interaction’ are continuous, linear covariates. For each patient, the error terms from the on-treatment visits represent the within-patient variability, and are assumed to follow a multivariate normal distribution with an unstructured covariance matrix.

If the model fails to converge, the following covariance structures will be tested in order: ANTE(1)→ARH(1)→AR(1). The first model to converge will be used as the primary analysis. The Kenward-Roger approximation will be used to estimate the denominator degrees of freedom. Significance tests will be based on least squares means using a two-sided $\alpha = 0.05$ (two sided 95% confidence intervals).

Only the available data which were observed whilst patients were on treatment will be included in the analysis. Missing data are handled implicitly by the above statistical model, rather than by using any imputation.

Superiority will be tested using the p-value of the treatment effect and a two-sided 95% confidence interval for the treatment difference.

For Week 24 analysis, all levels for factor week up to Week 24 are to be considered in the model, i.e. Week 4, 8, 12, 18 and 24.

16.1.9 Documentation of statistical methods

Proprietary confidential information © 2019 Boehringer Ingelheim International GmbH or one or more of its affiliated companies

Boehringer Ingelheim

TSAP for BI Trial No: 1218.102

Page 33 of 47

Proprietary confidential information © 2019 Boehringer Ingelheim International GmbH or one or more of its affiliated companies

In addition, descriptive statistics for HbA1c over time are presented for FAS (OC),

7.5 SECONDARY ENDPOINT(S)

7.5.1 Key secondary endpoint(s)

This section is not applicable as no key secondary endpoint has been specified in the protocol.

7.5.2 (Other) Secondary endpoint(s)

Change from baseline in FPG after 24 weeks of treatment

Analysis of change from baseline in FPG will follow the strategy for the primary endpoint. MMRM will be used to analyse the mean change from baseline in FPG after 24 weeks of treatment.

FPG change from baseline = overall mean + baseline HbA_{1c} + treatment + type of insulin
+ week+ week by treatment interaction
+ baseline FPG
+ baseline FPG by week interaction
+ random error

The analysis will include the fixed categorical effects of treatment, type of insulin, week and treatment by week interaction, as well as the continuous, fixed covariates of baseline FPG, baseline HbA_{1c} and baseline FPG by week. An unstructured (co)variance structure will be used to model the within patients measurements. This analysis will be performed on FAS (OC).

Change from baseline in 2-hour PPG after 24 weeks of treatment

Change from baseline is calculated as the on-treatment value minus the baseline values. The descriptive statistics will be displayed based on MTT-set (OC).

As 2-hour PPG is only collected once on-treatment, an ANCOVA model will be fitted on the MTT-set (OC). The analysis will use the ANCOVA model used in the strategy for the sensitivity analysis of HbA_{1c}, with additional baseline 2-hour PPG as a continuous covariate.

2-hour PPG change from baseline = overall mean + baseline HbA_{1c} + treatment
+ type of insulin + baseline 2-hour PPG
+ random error

Proportion of patients with HbA_{1c} on treatment < 7.0% after 24 weeks of treatment

Logistic regression for the patients achieving HbA_{1c} < 7.0% at Week 24 will be performed on FAS (NCF); patients who do not complete 24 weeks of treatment will be considered non-responders. The model will include treatment, continuous baseline HbA_{1c} and type of insulin. Patients with baseline HbA_{1c} < 7.0% will be excluded from the analysis.

16.1.9 Documentation of statistical methods

Proprietary confidential information © 2019 Boehringer Ingelheim International GmbH or one or more of its affiliated companies

Boehringer Ingelheim

TSAP for BI Trial No: 1218.102

Page 35 of 47

Proprietary confidential information © 2019 Boehringer Ingelheim International GmbH or one or more of its affiliated companies

A frequency table with the number and percentage of patients with HbA1c < 7.0% at Week 24 in each treatment group will also be presented based on FAS (NCF).

Proportion of patients with HbA1c on treatment < 6.5% after 24 weeks of treatment

Logistic regression for the patients achieving HbA1c < 6.5% at week 24 will be performed on FAS (NCF); patients who do not complete 24 weeks of treatment will be considered non-responders. The model will include treatment, continuous baseline HbA1c and type of insulin. Patients with baseline HbA1c < 6.5% will be excluded from the analysis.

A frequency table with the number and percentage of patients with HbA1c < 6.5% at week 24 in each treatment group will also be presented based on FAS (NCF).

Proportion of patients with HbA1c lowering by at least 0.5% after 24 weeks of treatment

Logistic regression for the patients achieving lowering of HbA1c by at least 0.5% from baseline at Week 24 will be performed on FAS (NCF); patients who do not complete 24 weeks of treatment will be considered non-responders. The model will include treatment, continuous baseline HbA1c and type of insulin.

Frequencies regarding the number and percentage of patients with lowering of HbA1c by at least 0.5% from baseline at Week 24 in each treatment group will be also be presented based on FAS (NCF).

The analyses for further safety endpoints are specified in [Section 7.8.1](#).

7.7 EXTENT OF EXPOSURE

Exposure to study drug will be calculated in days as (study drug stop date – study drug start date + 1) and will be tabulated as a frequency table with categorized treatment duration. In addition, median exposure and the number of patient years of exposure will be given per treatment (calculated as the sum of days over all patients per treatment group divided by 365.25).

7.8 SAFETY ANALYSIS

All safety analyses will be performed on the TS. All safety data will be displayed and analysed using descriptive statistical methods. No formal inferential analysis is planned for safety comparison.

7.8.1 Adverse events

The analysis of AEs will be descriptive in nature. All analysis of AEs will be based on the number of patients with AEs (not the number of AEs) according to the BI standards (3). For this purpose, AE data will be combined in a 2-step procedure into AE records.

Processing of individual AE information

In a first step, for analysis multiple AE occurrence data on the CRF will be collapsed into an AE provided that all of the following applies:

- The same lowest level term is reported for the occurrences.
- The occurrences are time-overlapping or time-adjacent (time-adjacency of 2 occurrences was given if the second occurrence started on the same day or on the day after the end of the first occurrence).
- Treatment does not change between the onset of the occurrence OR treatment changes between the onset of the occurrences, but no deterioration is observed for the later occurrence.

Assignment of AEs to treatments

In a second step, AE episodes will be condensed into AE records provided that the episodes are reported with the same term on the respective MedDRA level and that the episodes are assigned to the same treatment.

The analysis of AEs will be based on the concept of treatment emergent AEs. To this end, all AEs occurring between start of treatment and end of REP will be considered

16.1.9 Documentation of statistical methods

Proprietary confidential information © 2019 Boehringer Ingelheim International GmbH or one or more of its affiliated companies

Boehringer Ingelheim

TSAP for BI Trial No: 1218.102

Page 39 of 47

Proprietary confidential information © 2019 Boehringer Ingelheim International GmbH or one or more of its affiliated companies

‘treatment-emergent’. The REP is defined as a period of 7 days after the last dose of trial medication. That means that all AEs occurring between first drug intake till last drug intake + residual effect period (REP) will be assigned to the randomised treatment. All AEs occurring before first drug intake will be assigned to ‘screening’ and all AEs occurring after the REP will be assigned to ‘post-treatment’ (for listing only). For details on the treatment definition, see [Section 6.1](#).

In general, in-text AE tables will only present AEs assigned to the randomised treatments. End-of-text tables will display in addition AEs observed ‘pre-treatment’ (including AEs observed during screening and placebo run-in regardless of treatment group) and AEs observed during post-treatment regardless of treatment group.

Analysis of other significant AEs

According to ICH E3 ([1](#)), AEs classified as ‘other significant’ needs to be reported and will include those non-serious and non-significant AEs with

- (i) ‘action taken = discontinuation’ or ‘action taken = reduced’ or
- (ii) marked haematological and other lab abnormalities or lead to significant concomitant therapy as identified by the Clinical Monitor / Investigator at a Medical Quality Review Meeting (MQRM).

AE summaries

An overall summary of AEs will be presented.

The frequency of patients with adverse events will be summarised by treatment, primary system organ class (SOC) and preferred term (PT). Separate tables will be provided for patients with other significant adverse events according to ICH E3 ([1](#)), for patients with AESI, for patients with AEs leading to discontinuation, for patients with drug-related AEs and for patients with serious adverse event (SAE). The system organ classes will be sorted alphabetically, and preferred terms will be sorted by frequency (within SOC).

The frequency of patients with AEs will also be summarised by subgroups, including age, gender, background therapy and renal function. The details of the subgroups can be found in [Table 6.4: 1](#).

Additional AE analyses

Analysis of hypoglycaemic events

The investigator will record for each AE whether it represents a hypoglycaemic event and if so, record additional information to assess the intensity of the hypoglycaemic event. On the basis of this information the hypoglycaemic event will be classified as:

- investigator defined hypoglycaemic AE
 - hypoglycaemic AE with PG \leq 70 mg/dL (\leq 3.9 mmol/L) or severe hypoglycaemic AE (= confirmed hypoglycaemic AE)

16.1.9 Documentation of statistical methods

Proprietary confidential information © 2019 Boehringer Ingelheim International GmbH or one or more of its affiliated companies

Boehringer Ingelheim

TSAP for BI Trial No: 1218.102

Page 40 of 47

Proprietary confidential information © 2019 Boehringer Ingelheim International GmbH or one or more of its affiliated companies

- hypoglycaemic AE with PG < 54 mg/dl (≤ 3.0 mmol/L) or severe hypoglycaemic AE
- severe hypoglycaemic AE
- investigator defined symptomatic hypoglycaemic AE or severe hypoglycaemic AE
 - symptomatic hypoglycaemic AE with PG ≤ 70 mg/dL (≤ 3.9 mmol/L) or severe hypoglycaemic AE
 - symptomatic hypoglycaemic AE with PG < 54 mg/dL (≤ 3.9 mmol/L) or severe hypoglycaemic AE
 - severe hypoglycaemic AE

Asymptomatic hypoglycaemic events which are not considered to be an adverse events by the investigator and which have plasma glucose concentration ≥ 3.0 mmol/L and ≤ 3.9 mmol/L (≥ 54 mg/dL and ≤ 70 mg/dL) will be recorded by the investigator on a separate eCRF page.

Based on the above definition, different tables will be shown for (i) patients with investigator defined hypoglycaemic AEs, (ii) patients with any hypoglycaemia (investigator defined hypoglycaemic AE or asymptomatic hypoglycaemia not reported as AE), (iii) patients with any asymptomatic hypoglycaemia (investigator defined asymptomatic hypoglycaemic AE or asymptomatic hypoglycaemia not reported as AE). Each table will include total number of hypoglycaemic events, number of episodes per patient, minimum glucose level of worst episode, and time to onset of first episode.

Furthermore, patients with investigator defined hypoglycaemic AEs and confirmed hypoglycaemic AE will be tabulated by treatment group. A subgroup analysis with respect to age and rescue therapy will be performed.

The impact of treatment on the occurrence of patients with investigator defined hypoglycaemic AEs will also be explored using a logistic model involving treatment, continuous baseline HbA_{1c}, and type of insulin. Time to the onset of the first investigator defined hypoglycaemic AE will be analysed by Kaplan-Meier estimates.

Analysis of protocol specified AEs (=events of special interest)

As defined in protocol, the following events are considered as adverse events of special interest (AESI):

- Hypersensitivity reactions such as angioedema, angioedema-like events, and anaphylaxis
- Skin lesions such as exfoliative rash, skin necrosis, or bullous dermatitis
- Hepatic injury as defined by the following alterations of hepatic laboratory parameters:
 ≥ 3 fold ULN of AST and/or ALT in combination with an elevation of total bilirubin > 2 fold ULN measured in the same blood draw sample, hepatitis, hepatic injury, jaundice and potential Hy's Law cases

16.1.9 Documentation of statistical methods

Proprietary confidential information © 2019 Boehringer Ingelheim International GmbH or one or more of its affiliated companies

Boehringer Ingelheim

TSAP for BI Trial No: 1218.102

Page 41 of 47

Proprietary confidential information © 2019 Boehringer Ingelheim International GmbH or one or more of its affiliated companies

- Renal adverse events such as acute renal failure
- Pancreatitis (refer to the ISF)
- Pancreatic cancer

The categories and events included as AESIs may change over time. The definitions, including SMQs for the AESIs will be maintained on project level. All AESIs defined in the CTP are presented in the CTR. If further AESIs have been defined, they will also be included into the CTR.

For each AESI, the frequency of patients with the respective AESI will be summarised by treatment, user-defined AE category and preferred term.

Cardiovascular and neurological events qualifying for external adjudication by the Clinical Event Committee (CEC)

An independent external CEC regularly reviews events suspect of stroke, myocardial ischemia (incl. myocardial infarction), cardiovascular death and evaluates whether pre-specified criteria for these adjudication endpoints are met. Details on composition of the CEC, responsibilities and clinical event definitions are provided in a separate CEC Charter.

The CEC will be provided with additional, specified background material on the patients with these events and perform an assessment of the events.

Frequency tables will be provided for the preferred terms in the specified SMQs of events and for the adjudication endpoints.

Pancreatic events qualifying for external adjudication by the Clinical Event Committee (CEC)

An independent external CEC regularly reviews events suspect of acute pancreatitis, chronic pancreatitis, Asymptomatic Pancreatic Hyperenzymemia and Pancreatitis Malignancy and evaluates whether pre-specified criteria for these adjudication events are met. Details on composition of the CEC, responsibilities and clinical events definitions are provided in a separate CEC charter.

The CEC will be provided with additional, specified background material on the patients with these events and perform an assessment of the events.

Frequency tables will be provided for the preferred terms in the specified SMQs of events and for the adjudication endpoints.

7.8.2 Laboratory data

The analyses of laboratory data will be descriptive in nature and will be based on BI standards (4). All analyses will be based on TS.

16.1.9 Documentation of statistical methods

Proprietary confidential information © 2019 Boehringer Ingelheim International GmbH or one or more of its affiliated companies

Boehringer Ingelheim

TSAP for BI Trial No: 1218.102

Page 42 of 47

Proprietary confidential information © 2019 Boehringer Ingelheim International GmbH or one or more of its affiliated companies

Baseline for safety laboratory parameters will be the last available measurement before the start of randomised study drug. Laboratory values taken up to 7 days after the last administration of randomised study drug will be considered as on-treatment.

Laboratory values will be compared to their reference ranges and frequency tables will be provided for the number of patients within and outside the reference range at baseline and the last measurement on treatment. Descriptive statistics will be provided by treatment group for baseline, on-treatment values and for changes from baseline. Frequency tables will summarise the number of patients with potentially clinically significant abnormalities.

Specific considerations for hepatic parameters

To support analyses of liver related adverse drug effects, *Potential Hy's law* cases are defined by the combination of the following events within a time span of 30 days:

- Any on-treatment value of ALT or AST (or both) ≥ 3 times upper limit of normal (ULN) with
- Total bilirubin $\geq 2 \times$ ULN and
- Alkaline phosphatase $\leq 2 \times$ ULN

The start of the 30 day time span is triggered by each liver transaminase elevation above the defined thresholds.

Patients who fulfil one or two of the criteria for ALT/AST or total bilirubin elevation above for a potential Hy's law case and has no information available for the remaining parameter(s) at the same timepoint or within the 30 day time windows will be considered for presentation of potential Hy's law lab constellation as well.

All calculations for the grading will be based on the originally measured laboratory values and the ULNs given by the laboratory, not on normalised values with BI standard reference ranges.

Specific considerations for amylase and lipase

In order to support screening for highly increase amylase and/or lipase values in regards to the ULN, specific transition tables are defined. These transition tables check for erased values, values above the twofold ULN and values above the threefold ULN either at the end of treatment or at the peak value on treatment.

All calculations for the underlying grading will be based on the originally measured laboratory values and the ULNs given by the laboratory, not on normalised values with BI standard reference ranges.

Specific renal endpoints

The glomerular filtration rate (GFR) will be derived from serum creatinine* values based on the standard MDRD formula:

16.1.9 Documentation of statistical methods

Proprietary confidential information © 2019 Boehringer Ingelheim International GmbH or one or more of its affiliated companies

Boehringer Ingelheim

TSAP for BI Trial No: 1218.102

Page 43 of 47

Proprietary confidential information © 2019 Boehringer Ingelheim International GmbH or one or more of its affiliated companies

$eGFR \text{ (ml/min/1.73 m}^2\text{)} = 175 \times [\text{Screatinine (}\mu\text{mol/L)/88.4}]^{-1.154} \times [\text{age}]^{-0.203} \times [0.742 \text{ if patient is female}] \times [1.212 \text{ if patient is of African origin}]$

*: creatinine methods calibrated to an IDMS reference method

Calculation of age in the determination of eGFR will be done by:

$$\text{Age} = (\text{laboratory assessment date} - \text{date of birth} + 1) / 365.25.$$

To support analysis of renal function, eGFR throughout the trial will be categorised according to the following MDRD staging:

Table 7.8.2: 1 MDRD staging

| Stage | eGFR (mL/min/1.73m ²) | Description | Label for displays |
|-------|-----------------------------------|--|------------------------|
| 1 | ≥90 | Normal renal function | ≥90 (normal) |
| 2 | 60 to <90 | Mild renal impairment | 60 to <90 (mild) |
| 3 | 45 to <60 | Moderate renal impairment A | 45 to <60 (moderate A) |
| 4 | 30 to <45 | Moderate renal impairment B | 30 to <45 (moderate B) |
| 5 | <30 | Sever renal impairment or endstage renal disease | <30 (end stage) |

Fasting plasma glucose will be included in the safety analyses with respect to the reference range and in the analysis of possible clinically significant abnormalities. Descriptive statistics over time and further statistical analyses will be part of the efficacy analysis.

Urine albumin and urine creatinine do not have a reference range and are determined to calculate the albumin / creatinine ratio. Only the albumin /creatinine ratio will be analysed as for albumin and creatinine no normalised values can be derived. In cases where urine albumin values are reported to be below the quantification limits (e.g. < 3 mg/L) the albumin / creatinine ratio is determined as missing and will not be replaced by estimated values.

Reported original negative quantitative safety laboratory values will be excluded from analyses (consistently from all tables and listings). (This does not apply to normalised values, which will be used.)

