16.1.9 Documentation of statistical methods

Proprietary confidential information © 2019 Boehringer Ingelheim International GmbH or one or more of its affiliated companies

Boehringer Ingelheim

TSAP for BI Trial No: 1218.102

Proprietary confidential information © 2019 Boehringer Ingelheim International GmbH or one or more of its affiliated companies

Table 6.6: 1 Summary of imputation methods for efficacy endpoints

| Imputation method | Endpoint | Handling of missing values | Handling of values after rescue therapy |
|-------------------|---|---|--|
| OC | Continuous and binary endpoints | No imputation | Excluded (considered missing). One picked value per visit. |
| NCF | Binary endpoints derived from continuous endpoints (e.g. HbA _{1c} <7.0%) | Missing values after premature discontinuation of study drug are considered failure (endpoint not achieved). Missing values with subsequent present on-treatment values will be imputed based on the interpolated values for the underlying continuous endpoint. | Values after the start of rescue therapy are imputed as failure. |

Safety and other variables

Missing safety data will not be replaced, but an analysis of the change from baseline to the last available value under treatment and the minimum and maximum post baseline will be determined for quantitative safety laboratory variables. In general, the last measurement taken between the first intake of randomised trial drug and drug-stop date + 7 days will be analysed as the last value on-treatment.

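### Coding the urine albumin/creatinine ratio as missing when albumin is below quantification makes reported ratios too high and the baseline within-range share too low

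*SAP*

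**What the plan says.** SAP 7.8.2, under the specific renal endpoints, gives an explicit rule. When urine albumin is reported below quantification (3 mg/L is the example), the ratio "ratio is determined as missing and will not be replaced by estimated values". The same paragraph closes the alternative route: only the albumin / "creatinine ratio will be analysed as for albumin and creatinine no normalised values can be derived". A low albumin result therefore appears in no other albuminuria summary.

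The other passages that determine what happens to these results are:

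- SAP 7.8.2, level summaries: "Descriptive statistics will be provided by treatment group for baseline, on-treatment values and for changes from baseline". The same paragraph plans tables of patients within and outside the reference range at baseline and at the last measurement on treatment.
- SAP 7.8.2, baseline: "Baseline for safety laboratory parameters will be the last available measurement before the start of randomised study drug".
- SAP 6.6, safety variables: missing data are not replaced, but "an analysis of the change from baseline to the last available value under treatment" is planned for quantitative laboratory variables.
- SAP 7, percentages: "Percentages will be based on all patients in the respective patient set whether they have non-missing values or not". A *Missing* row "will be displayed if and only if there are actually missing values".
- Protocol 5.3.3: the central laboratory calculates the ratio.

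Nothing in the available text counts, flags or bounds the below-limit results.

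**The concern.** A below-limit albumin is a measurement. With creatinine measured in the same sample, the ratio has a known upper bound. The rule turns that information into a missing value, and does so only for low results, so the missingness depends on the value itself.

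Three consequences follow:

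- Means and medians of the retained ratios are too high.
- Patients known to be low are left out of the within-range count and merged with patients whose sample was never taken.
- A visit-level change is lost when either of its two values is below the limit.

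At stake is whether the albuminuria tables in the trial report describe the patients correctly. The efficacy result is not involved.

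**Working it through.** The plan states no figure for this point, so there is none to reproduce.

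**1. Bound.** With albumin below 3 mg/L, ratio < 3 / creatinine (g/L):

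| Urine creatinine | Ratio must be below |
|---|---|
| 10 mg/dL (0.1 g/L) | 30 mg/g |
| 50 mg/dL (0.5 g/L) | 6 mg/g |
| 100 mg/dL (1.0 g/L) | 3 mg/g |

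The dropped results are low ones. They lie within an assumed 30 mg/g limit unless the urine is extremely dilute.

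**2. Direction, without a distribution.** Let b be the share below quantification (all truly within range) and q the share truly above range.

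- True within-range share: 1 − q.
- Shown over all patients (SAP 7 rule): 1 − q − b, too low whenever b > 0.
- Shown over non-missing: (1 − q − b)/(1 − b), too low whenever b > 0 and q > 0.
- Above-range share over all patients: q, unchanged.

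Example with q = 20% and b = 20%: true 80%; shown 60% over all patients, or 0.60/0.80 = 75% over non-missing.

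**3. Size at baseline.** Assumptions not in the documents: limit 3 mg/L applied throughout, cut-off 30 mg/g, ratio log-normal with log-SD 1.3, creatinine log-normal with median 1 g/L and log-SD 0.5. Albumin is then log-normal with log-SD √(1.3² + 0.5²) = 1.393.

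- b = Φ(ln(3/median)/1.393), and the true within-range share = Φ(ln(30/median)/1.3).
- At median 15: b = Φ(−1.155) = 12.4% and true share = Φ(0.533) = 70.3%. Shown: 70.3 − 12.4 = 57.9% over all patients, or 57.9/87.6 = 66.1% over non-missing.

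| True median (mg/g) | Missing | Reported median | True mean → reported | Within range: true | Shown, all patients | Shown, non-missing |
|---|---|---|---|---|---|---|
| 15 | 12% | 18.4 | 34.9 → 39.5 | 70% | 58% | 66% |
| 8 | 24% | 11.9 | 18.6 → 23.8 | 85% | 60% | 80% |
| 5 | 36% | 9.1 | 11.6 → 17.1 | 92% | 56% | 87% |

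Medians and means come from simulation. With 103 per arm, about 13/25/37 patients would be affected. A mild case (median 20, log-SD 1.0) gives 4.5% missing, a reported median of 21.1, and 66% within range shown as 61% (all) or 64% (non-missing).

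**4. Last measurement on treatment.** With one on-treatment urine result, the shortfall equals that at baseline. If there are several and an earlier quantifiable value stands in for a below-limit last one, it shrinks. I assumed five on-treatment results, no shift, and within-patient correlations of 0.75 (log ratio) and 0.5 (log creatinine). The within-range share is then shown as about 68/77/77% over all patients, or 69/83/90% over non-missing, against 70/85/92%. The on-treatment median is 16.1/9.9/7.5 against 15/8/5.

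**5. Change from baseline.** With no true shift, mean and median change stay within 0.06 mg/g of zero in the simulation. With one value before and one after, 18/34/47% of pairs are lost (7% in the mild case).

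**The case against.** The strongest reply has four parts.

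**Safety data are not imputed.** Protocol 7.5 and SAP 6.6 both say so, and SAP 7.8.2 can be read as applying that principle to a laboratory-calculated ratio. This stands against half-limit substitution, which is arguably imputation and brings its own artefacts: change between two below-limit visits would reflect only creatinine. It does not answer the main point. Here the rule creates the missing value, and classifying a result by its bound, or counting it, imputes nothing.

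**The sponsor's laboratory standard may govern the display.** SAP 7.8.2 cites one, and it is not available. It could settle denominators or the *Missing* row. However, the SAP states its own explicit rule for this ratio, and the upward pull on levels does not depend on the denominator.

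**The sizes are assumed.** They are. The documents give no albumin distribution, no ratio reference limit and no visible urine schedule. Only the direction is certain, and the mild case is small.

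**It hardly matters.** The analysis is descriptive, the rule is the same in both arms, and N of non-missing values is displayed, so the loss is partly visible. This stands and limits the weight of the point. N alone does not separate low results from absent samples.

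A reader might also infer that the baseline shortfall applies to both range tables. The documents do not support that, because the on-treatment table may draw on several results.

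**Conclusion.** The point holds as a minor one. As written, the rule makes ratio levels too high and the baseline within-range share too low. The direction needs only that some results fall below quantification and that their bounds lie within range (for the non-missing denominator, also that some patients are above range). The sizes rest on the assumptions listed in the working and run from negligible to large. The last-on-treatment table is affected as much as baseline or less, depending on the schedule.

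Two stronger readings should be resisted:

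- **That abnormal results are over-reported.** Under the SAP's all-patients denominator, the above-range share at baseline is exactly unchanged. In the five-result illustration it moves by only about 0.2 percentage points. It is inflated only over non-missing values (29.7% becomes 33.9% at median 15).
- **That the treatment comparison is biased.** The rule is identical in both arms, and change is not biased without a true shift. A true shift could be distorted either way, exaggerated if proportional and understated if additive, but nothing in the documents suggests such a shift.

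No primary or secondary endpoint, alpha or power is affected.

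**What to change.** In SAP 7.8.2, replace the missing rule with the following:

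- **(a)** A below-limit result counts as within range when limit/creatinine is within range. Otherwise it is shown as below quantification, not classifiable. In the illustrations almost no bound reached 30 mg/g.
- **(b)** A below-limit result stands as the measurement for its visit, including the last one, and is not replaced by an earlier quantifiable value.
- **(c)** The number below the limit is reported by arm and visit, separately from samples not taken.
- **(d)** Medians and quartiles rank below-limit results as lowest. This is approximate, since their bounds vary with creatinine. A quartile that falls among them is shown as below quantification.

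Half-limit substitution for means and changes is optional, as a flagged supplementary summary. It would have to be reconciled with the no-imputation statements in Protocol 7.5 and SAP 6.6.

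The cost is a short text change and a small amount of programming, using albumin and creatinine results already planned for collection. The downside is that sponsor-derived categories sit beside laboratory-calculated ratios, so they need a flag.
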